3.2 Study Population

A total of 51 healthy Japanese and non-Japanese male and female subjects will be enrolled in this clinical study. Cohorts 1-4 may have up to 36 subjects enrolled (a total of up to 16 Japanese subjects and up to 20 non-Japanese subjects). Cohort 5 may have up to 15 subjects (N=15) with a targeted but non-mandatory enrollment of up to 5 Japanese subjects. Detailed lists of inclusion and exclusion criteria are shown in Sections 4.2 and 4.3 of the CSP.

3.3 Statistical Basis for Sample Size

The sample size for this FIH Phase 1 study was not based on formal statistical determinations. The sample size for this study was chosen in consideration of limiting exposure to this new chemical entity while providing sufficient information to evaluate the safety and tolerability of VIS649 in a Phase I setting.

3.4 Randomization

Randomization and blinding will occur according to a core randomization list administered by the site's unblinded pharmacist.

PAREXEL International
Statistical Analysis Plan

Prior to dosing on Day 1, all screened and eligible subjects will be assigned a randomization number in accordance with the randomization code generated by PAREXEL International. If subjects are withdrawn prematurely from the study and are replaced under the direction of the Sponsor, then a replacement randomization number will be assigned. Cohort, randomization numbers and replacement numbers are listed in Table 3.

Table 3 Randomization Numbers and Treatment Assignment

Dose Group	Randomization Numbers	Replacement Numbers	Treatment Assignment	
Cohort 1	[REDACTED]	[REDACTED]	0.5 mg/kg VIS649 (N=7)	Placebo (N=2)
Cohort 2	[REDACTED]	[REDACTED]	2.0 mg/kg VIS649 (N=7)	Placebo (N=2)
Cohort 3	[REDACTED]	[REDACTED]	6.0 mg/kg VIS649 (N=7)	Placebo (N=2)
Cohort 4	[REDACTED]	[REDACTED]	12 mg/kg VIS649 (N=7)	Placebo (N=2)
Cohort 5	[REDACTED]	[REDACTED]	VIS649 6.0 mg/kg plus vaccine (N=10)	Placebo plus vaccine (N=5)

No more than one Japanese subject per cohort may be randomized to receive placebo in cohorts 1-4. No more than two Japanese subjects may be randomized to receive placebo in cohort 5.

3.5 Subject Withdrawal and Replacement

All subjects who withdraw from the study with an ongoing AE must be followed until the event is resolved or deemed stable. If a subject withdraws prematurely after dosing, all data to be collected prior to discharge from the clinical site should be collected at the time of premature discontinuation or at the scheduled discharge. Subject participation may be terminated prior to completing the study and the reason recorded as follows:

- Adverse event
- Protocol violation
- Loss to follow-up
- Subject withdrew consent at own request

PAREXEL International Statistical Analysis Plan

- Other

Once a randomization number has been allocated to one subject, it may not be assigned to another subject. If subjects withdrawn prematurely from the study and are replaced under the direction of the Sponsor, then a replacement randomization number will be assigned. A replacement randomization code will be generated such that replacement subjects are assigned to the same treatment as the discontinued subjects. The replacement randomization code will differ only in randomization numbers, which will be 4-digit numbers [REDACTED]

3.6 Termination of the Clinical Study

The clinical study may be terminated at the Sponsor's discretion also in the absence of such a finding. Conditions that may warrant termination of the clinical study include, but are not limited to:

- The discovery of an unexpected, relevant or unacceptable risk to the subjects enrolled in the clinical study;
- Failure to enroll subjects at the required rate;
- A decision of the Sponsor to suspend or discontinue development of the study drug.

4. STATISTICAL ANALYSIS CONVENTIONS

4.1 Analysis Variables

4.1.1 Demographic and Background Variables

The following demographic and anthropometric information will be recorded:

- Date of informed consent
- Age
- Ethnicity: Japanese, Non-Japanese (Hispanic, Latino, Caucasian, etc.)
- Race: White, Black or African American, Asian, American Indian and Alaska Native, Native Hawaiian and Other Pacific Islander

PAREXEL International Statistical Analysis Plan

- Height, without shoes (cm)
- Body weight, without shoes (kg)
- BMI (kg/m²)
- History of drug abuse
- History of alcohol abuse
- Smoking history
- History of caffeine use (or other stimulating beverages)
- History of blood or plasma donation

Medical History includes:

- General medical history
- Medication history
- Reproductive history

All medical history will be coded using Version 21.1 of the Medical Dictionary for Regulatory Activities (MedDRA).

4.1.2 Concomitant Medication

Any medicinal product, prescribed or OTC, including herbal and other nontraditional remedies, is considered a concomitant medication. Prior and concomitant medication use will be recorded for the 30 days prior to the Screening Visit until the End-of-Study Visit.

Complete or partial dates will be handled as follows:

- Medication with completely missing start date will be considered as prior.
- Medication with a partial start date will be considered as prior unless the available portion of the date indicates otherwise.
- Medication with a missing start time where the start date is the same as the dosing date will be considered as prior.

PAREXEL International Statistical Analysis Plan

- Medication with completely missing end date will be considered as concomitant.
- Medication with a partial end date will be considered as concomitant unless the available portion of the date indicates otherwise.
- Medication with a missing end time and end date that is the same as the dosing date will be considered as concomitant.

Medications with missing date and/or time information will have the missing information identified by NK in the listings (where NK = Not Known).

Concomitant medication will be coded using the World Health Organization-Drug Dictionary (WHO Drug Version Global September 2018 B3) and will be classified by Anatomical Therapeutic Chemical (ATC) categories.

4.1.3 Exposure to the Investigational Medicinal Product (IMP)

Data of study drug administration will be recorded, including the infusion date, start and stop times of the infusion, total volume infused, site of infusion, and arm used.

For cohort 5 participants, an additional single dose of tetanus/diphtheria vaccine will be injected intramuscularly into the opposite arm of the one with study drug administration, its administration data will be collected.

4.1.4 Safety Variables

4.1.4.1 Adverse Events

Adverse event reporting will begin for each subject from Baseline (Day -1) and will continue until the End-of-study Visit. All serious adverse events (SAEs) will be recorded from signing of the ICD until the End-of-study Visit.

A treatment-emergent adverse event (TEAE) is defined as an AE that begins or that worsens in severity after at least one dose of the study drug has been administered.

The Principal Investigator will assess all AEs for severity in accordance with the standard ratings: Mild, Moderate and Severe. Details can be found in the section 6.2.1.3.1 of the CSP.

The Principal Investigator will assess the causality/relationship between the study drug and the AE based on the categories of Related, Probably related, Possibly related, Unlikely to be related, and Unrelated. The causality for each AE will be summarized as “related” (Related, Probably related, and Possibly related) and “not related” (Unlikely to be related, and Unrelated). Details are described in the section 6.2.1.3.2 of the CSP.

AEs for cohort 5 will be assessed for relationship to vaccine and its administration separately from relationship to study drug and its administration (see sections 1.3 and 6.2.1.3 of the CSP for details).

All AEs will be coded using the Medical Dictionary for Regulatory Activities (MedDRA) version 21.1 or higher.

4.1.4.2 Clinical Laboratory Tests

The following safety laboratory parameters will be measured (Table 2) in the study.

Table 4 Clinical Laboratory Assessments

Hematology	
White blood cell (WBC) count	Neutrophils (percentage and absolute count)
Red blood cell (RBC) count	Lymphocytes (percentage and absolute count)
Hemoglobin (Hb)	Monocytes (percentage and absolute count)
Hematocrit (HCT)	Eosinophils (percentage and absolute count)
Mean corpuscular volume (MCV)	Basophils (percentage and absolute count)
Mean corpuscular hemoglobin (MCH)	Platelet count
Mean corpuscular hemoglobin concentration (MCHC)	RBC distribution width
Coagulation	
Prothrombin time (PT)	International Normalized Ratio (INR)
Activated partial thromboplastin time (aPTT)	
Clinical Chemistry	
Alanine aminotransferase (ALT)	Glucose
Albumin	Lactate dehydrogenase (LDH)
Alkaline phosphatase (ALP)	Phosphorus
Aspartate aminotransferase (AST)	Potassium
Blood urea nitrogen (BUN)	Sodium
Calcium	Total bilirubin
Chloride	Total protein
Cholesterol	Triglycerides
Creatinine	Uric acid

PAREXEL International
Statistical Analysis Plan

Gamma glutamyl transferase (GGT)	FSH (Screening Visit only; all female subjects)
Urinalysis	
Bilirubin	Blood
Glucose	pH and specific gravity
Ketones	Protein
Leukocytes	Urobilinogen
Nitrite	Microscopic (only for abnormal urine stick test findings)
Viral Serology	
Human immunodeficiency virus (HIV) (Types 1 and 2) antibodies	Hepatitis C virus antibody (anti-HCV)
Hepatitis B surface antigen (HBsAg)	
Serology	
Tetanus/diphtheria serology	
Urine Drug Screening and Cotinine Test	
Amphetamines	Cocaine
Barbiturates	Opiates
Benzodiazepines	Phencyclidine
Cannabinoids	Cotinine
Urinary creatinine (to exclude dilution effect)	Ethanol
Pregnancy Testing	
Serum/urine human beta chorionic gonadotrophin (women of childbearing potential only)	

4.1.4.3 Vital Signs

The following vital signs measurements will be obtained at the time points detailed in the Schedule of Assessments in Table 1.

- Systolic blood pressure (SBP) [mmHg]
- Diastolic blood pressure (DBP) [mmHg]
- Heart Rate (bpm)
- Respiratory rate (breaths per minute)
- Temperature [°C]

Blood pressure and heart rate recordings will be made after the subject has been in a seated or supine position and at rest ≥ 5 minutes.

4.1.4.4 Standard 12-lead Electrocardiograms

12-lead ECGs will be performed at the time points detailed in the Schedule of Assessments in Table 1. The following ECG parameters will be recorded:

- RR-interval (msec)
- PR (PQ)-interval (msec)
- QRS-duration (msec)
- QT-interval (msec)
- QT-interval corrected using the Fridericia's correction (QTcF) (msec)
- Heart rate (HR) (beats per minute [bpm])

The 12-lead ECGs will be performed after the subject has been resting supine for \geq 5 minutes.

All ECGs must be evaluated by a qualified physician as "Normal", "Abnormal, NCS" or "Abnormal, CS", the abnormalities will be presented.

4.1.4.5 Physical Examination

The full physical examinations and brief physical examinations will be conducted by a licensed physician in accordance with the Schedule of Assessments in Table 1. The details of the full/brief physical examinations are described in the section 6.2.5 of the CSP.

4.1.5 Pharmacokinetic Variables

Blood samples for the determination of the concentration of VIS649 will be collected on Day 1 (prior to the start of infusion, at the end of infusion (60 minutes) and at 2 hours, 8 hours and 24 hours post end of infusion), Days 3, 7, 14, 28, 42, 56, 70, and 112. For details please refer to the Schedule of Assessments in Table 1.

The following PK parameters will be determined for VIS649 in serum samples following single dose administration:

PAREXEL International
Statistical Analysis Plan

Table 5 Pharmacokinetic Parameters after Single Dose Administration

Parameter	Definition
C_{max}	Maximum serum VIS649 concentration determined directly from the concentration-time profile
T_{max}	Time of maximum serum VIS649 concentration determined directly from the concentration-time profile
AUC_{0-112d}	Area under the concentration-time curve from pre-dose (time 0) to the concentration on day 112
AUC_{0-last}	Area under the concentration-time curve from pre-dose (time 0) to the last quantifiable concentration
AUC_{0-inf}	Area under the concentration-time curve from pre-dose (time 0) extrapolated to infinite time [REDACTED]
$t_{1/2}$	Terminal elimination half life
λ_Z	First-order terminal elimination rate constant [REDACTED] [REDACTED] [REDACTED] [REDACTED]
CL	Clearance [REDACTED]
V_d	Volume of distribution [REDACTED]

4.1.5.1 Pharmacokinetic Parameter Calculation Methods

[REDACTED]
[REDACTED]
[REDACTED]
[REDACTED]
[REDACTED]
[REDACTED]
[REDACTED].

PK parameters will be estimated according to the following guidelines:

PAREXEL International
Statistical Analysis Plan

- C_{\max} will be obtained directly from the concentration-time data.

- t_{\max} is the actual time at which C_{\max} is observed.

- λ_Z will be estimated at terminal phase

[REDACTED]

PAREXEL International
Statistical Analysis Plan

[REDACTED]
[REDACTED]

4.1.6 Pharmacodynamic (PD) Variables

Blood samples for PD parameters will be drawn in accordance with the Schedule of Assessments in Table 1.

Change from baseline will be calculated for each of following PD parameters:

- Immunoglobulin levels (total serum IgA, IgG and IgM)
- lymphocytes (and their subsets) for cohort 1-4
- Immunoglobulin subtypes (IgA and IgG), [REDACTED]
- [REDACTED]
[REDACTED]

Table 5 Immune Assessment B Cell Subsets, B

[REDACTED]
[REDACTED]
[REDACTED]
[REDACTED]
[REDACTED]

Immune Assessment B Cell Subsets, B

[REDACTED]
[REDACTED]
[REDACTED]
[REDACTED]
[REDACTED]

PAREXEL International
Statistical Analysis Plan

[REDACTED]

[REDACTED]

[REDACTED]

Table 6 Immunoglobulin Subtypes

IgA subtypes: [REDACTED]

IgG subtypes: [REDACTED]

And also time to recovery of total serum IgA, IgG and IgM will be analyzed, two measures will be used:

- 1) Time to return to normal range (for those parameters that fall below LLN).

[REDACTED]

[REDACTED]

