1.3. Risk-benefit Assessment

While VIS649 has not been evaluated in humans, the known effects of mAbs in humans suggest the following potential toxicities for single dose administration:

1. Infusion reactions: Anaphylaxis, fever, chills, rigors, nausea, vomiting, pain, headache, dizziness, shortness of breath, bronchospasm, hypotension, hypertension, pruritus, rash, urticaria, angioedema, diarrhea, tachycardia, and chest pain
2. Delayed allergic reactions: Serum sickness (i.e., urticaria, fever, general glandular enlargement, joint pains)
3. General: Injection site reaction

Mechanism based potential toxicities that might be anticipated based on VIS649 mechanism of action and preclinical studies include:

IgA suppression risks: VIS649 treatment is expected to reduce human IgA levels, with a predicted maximal reduction (with repeated dosing) to approximately 75% below baseline. In this single-ascending dose study, this degree of suppression is unlikely to be achieved, but it is anticipated that at least in the higher dose cohorts, IgA levels will be reduced below baseline, with effect persisting over weeks.

The normal range for serum IgA is approximately 70 to 400 mg/dL in adults [REDACTED]

[REDACTED]

[REDACTED]

Selective IgA deficiency (defined as persistently undetectable IgA, [REDACTED]) is the most common inherited immunodeficiency syndrome (occurring in about 1 in 500 Caucasian individuals). [3]. While this condition has heretofore been considered generally benign and is asymptomatic in the majority of patients, there is increasing recognition that selective IgA deficiency may be associated with recurrent sinopulmonary infection, allergy, autoimmunity and gastrointestinal microbiome perturbation [4, 5]. The risk for occurrence of these complications in the current study is low for multiple reasons: 1) IgA is expected to be suppressed, but not reduced to undetectable levels, 2) in this single dose-study, the effects on IgA levels are expected to be transient, and 3) the syndrome of selective IgA deficiency is often associated with additional immunologic impairments including T-cell disorders and common variable immunodeficiency syndrome.

IgG suppression risks: VIS649 is expected to have a moderate effect on serum IgG levels (with approximately 40% suppression-below-baseline nadir values predicted).

The normal range for serum IgG is approximately 600 to 1600 mg/dL in adults, [REDACTED]

[REDACTED]

[REDACTED]

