2.2.2 Pharmacodynamic Endpoints

- Changes in total serum IgG, IgA and IgM concentrations and time to recovery
- Changes in circulating lymphocyte populations in cohorts 1-4 only (this assessment will be done for all lymphocytes, and also for lymphocyte subsets that are noted to show changes from baseline).
-

Visterra Inc.
VIS649-101

Final 1.0
3/Jun/2019

TP-EP.BS-WW-001-05

Effective date: 29 Jul 15

Related to: SOP-EP-BS-WW-002

Page 15 of 68

PAREXEL International
Statistical Analysis Plan

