1. The first two subjects of each cohort will be discharged 24 hours (Day 2) after the study infusion. All other subjects are discharged on Day 2, 24 hours after study infusion. Discharge from the Phase 1 unit will not occur prior to performing the 24 h post infusion study procedures.

Visterra Inc.
VIS649-101

Final 1.0
3/Jun/2019

TP-EP.BS-WW-001-05
Effective date: 29 Jul 15
Related to: SOP-EP.BS-WW-002

PAREXEL International
Statistical Analysis Plan

2. Optional Visit at Week 20 is only to be made if immunoglobulin levels (IgG, IgM, or IgA) have not returned to normal range by Week 16; the Optional Visit at Week 24 is only to be made if immunoglobulin levels have not returned to normal range by Week 20. If immunoglobulin levels (IgG, IgM, or IgA) have not returned to normal range by Week 16 for one or more subjects, the entire cohort will complete Week 20 and Week 24.
3. Vitals signs at Screening and Day -1 will include height and weight, to permit estimated creatinine clearance calculation, as well as blood pressure (bp), heart rate (hr), respiratory rate (rr) and temperature. Subject weight will be measured after admission to the research unit (Day -1) and will be used by pharmacy staff for subject-specific dose calculation. Vital signs at other timepoints will be limited to temperature (Day -1 and Day 1 pre-dose only), bp, hr, and rr. Vital signs measurements on Day 1 will be recorded within 30 minutes prior to the start of the infusion, then every 15 minutes until the infusion is complete and post infusion at 60 minutes, 2 hours and 4 hours. On subsequent visits, vital signs will be recorded, as possible, at approximately the same time of day, if convenient. Post-dose bp should be based on the end of infusion time.
4. On Day 1 electrocardiograms will be done within 30 minutes prior to infusion and at the end of the infusion (+10 min).
5. On the day of study infusion (Day 1), blood samples for PK analysis will be collected prior to start of the infusion, at the end of infusion (60 minutes), and at 2 hours, 8 hours, and 24 hours post end of infusion. All subjects will have PK samples drawn on Days 3, 7, and Weeks 2 (Day 14), 4 (Day 28), 6 (Day 42), 8 (Day 56), 10 (Day 70), and 16 (112).

■ [REDACTED]
■ [REDACTED]
■ [REDACTED]

7. This sampling will not be done for cohort 5.
9. This sampling will be pre-vaccination in cohort 5.

PAREXEL International Statistical Analysis Plan

Cohorts are planned as follows:

Table 2 Cohorts and Dose Administration

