4.3.4 Missing Data

There will be no imputation of missing data done except for defining Treatment Emergent Adverse Event (TEAE) and for defining prior and concomitant classification.

4.3.4.1 Imputation of Partial Start Dates and Times in defining TEAE data:

Any AEs with incomplete start dates/times will be handled according the following rules for classification as treatment-emergent respectively. Such imputations will only be performed for these classifications:

- Adverse events with completely unknown start dates will be imputed with the date of dosing, unless the end date is known and prior to dosing; in that case the start date will be imputed as the date of Screening. Any AEs begin or worsen in severity on Day 1 are TEAEs.
- Adverse events with partially known start dates/times will be treated as follows:
 - Adverse events with unknown start times (but where the date is known) and where the start date is different to the dosing date, will be imputed with a time of 00:00 h for calculations. If the start date is the same as the dosing date the start time will be imputed to the dose time, so the AE is reported as treatment emergent.
 - If only the day is missing, then the day will be imputed with the first day of the month, unless the month and year in which the AE started is a month and year in which the study drug was administered, then the day will be imputed with the first day on which the study drug was administered in that month. If this results in a start date after the end date then the day will be imputed with the first day of the month.
 - If only the month is missing and the year is a year in which the study drug was administered, then the month will be imputed with the first month in which the study

PAREXEL International Statistical Analysis Plan

drug was administered. If this results in a start date after the end date of the AE then the month will be imputed with JAN. If the known year part is not a year in which the study drug was administered then the month will also be imputed with JAN.

- If both the day and month is missing and the year is a year in which the study drug was administered then the day and month will be imputed with the day and month of dosing. If this results in a start date after end date then the day and month will be imputed with 01JAN. If the year is not a year in which the study drug was administered then the day and month will also be imputed with 01JAN.

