4.3.8 Pharmacodynamic Variables

The analysis of the PD data will be based on the PD population.

For cohort 5, if number of either Japanese subjects or non-Japanese subjects is less than 3, cohort 5 won't be included in "by ethnicity" analysis.

As secondary endpoints, individual subject pharmacodynamics data of serum concentrations of Immunoglobulin levels (total IgA, IgG and IgM) will be listed [Listings 16.2.6.3.1 (observed) and 16.2.6.3.2 (change from baseline)], observed and change from baseline will be summarized descriptively by treatment [Tables 14.2.7.1 (Immunoglobulin)] and by ethnicity and treatment [Tables 14.2.7.2 (Immunoglobulin)].

Individual subject circulating lymphocytes and lymphocyte subsets will be listed [Listings 16.2.6.4.1 (observed) and 16.2.6.4.2 (change from baseline), and 16.2.6.5.1 (observed) and 16.2.6.5.2 (change from baseline) respectively]; observed values and change from baseline will be summarized descriptively by treatment [Tables 14.2.8.1 (lymphocytes), and 14.2.9.1 (lymphocyte subsets), separately] and by ethnicity and treatment [Tables 14.2.8.2 (lymphocytes), and 14.2.9.2 (lymphocyte subsets), separately]. This assessment will be done for all lymphocytes, and also for lymphocyte subsets that are noted to show changes from baseline. These analyses will be conducted for cohorts 1-4 only.

Individual observed value, change from baseline and percent change from baseline plots against time (Figures [Total IgA: 14.2.2.1.1, 14.2.2.1.2 and 14.2.2.1.3], [Total IgG: 14.2.2.2.1, 14.2.2.2.2, and 14.2.2.2.3], [Total IgM: 14.2.2.3.1, 14.2.2.3.2 and 14.2.2.3.3]), and individual observed value, change from baseline plots against time (Figures [Lymphocytes (cohorts 1-4 only): 14.2.2.4.1 and 14.2.2.4.2], and [Lymphocyte subsets (cohorts 1-4 only): 14.2.2.5.1 and 14.2.2.5.2]) will be produced by treatment with each subject being identifiable. The actual sampling time will be used in days on the x-axis.

Mean (\pm SD), mean change from baseline and percent mean change from baseline plots against time (Figures [Total IgA: 14.2.2.1.4, 14.2.2.1.5 and 14.2.2.1.6], [Total IgG: 14.2.2.2.4, 14.2.2.2.5 and

PAREXEL International

Statistical Analysis Plan

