Table 14.2.6.2.2 Pharmacokinetic Parameters of VIS649 Descriptive Statistics by Overall Subject ADA Classification by Treatment and Ethnicity (Pharmacokinetic Population)

Pharmacodynamic Data

Table 14.2.7.1 Summary of Pharmacodynamic Parameters by Treatment : Immunoglobulin (Pharmacodynamic Population)

Table 14.2.7.2 Summary of Pharmacodynamic Parameters by Ethnicity and Treatment : Immunoglobulin (Pharmacodynamic Population)

Table 14.2.7.3 Summary of Pharmacodynamic Parameters by Treatment : Immunoglobulin Subtypes (Pharmacodynamic Population)

Table 14.2.7.4 Summary of Pharmacodynamic Parameters by Ethnicity and Treatment : Immunoglobulin Subtypes (Pharmacodynamic Population)

Table 14.2.7.5 Summary of Pharmacodynamic Parameter by Treatment: APRIL (Pharmacodynamic Population)

Table 14.2.7.6 Summary of Pharmacodynamic Parameter by Ethnicity and Treatment: APRIL (Pharmacodynamic Population)

Table 14.2.7.7 Summary of Pharmacodynamic Parameter by Treatment: a-g IgA (Pharmacodynamic Population)

PAREXEL International
Statistical Analysis Plan

Table 14.2.7.8 Summary of Pharmacodynamic Parameter by Ethnicity and Treatment: a-g IgA (Pharmacodynamic Population)

Table 14.2.8.1 Summary of Pharmacodynamic Parameters by Treatment : Lymphocytes (Pharmacodynamic Population)

Table 14.2.8.2 Summary of Pharmacodynamic Parameters by Ethnicity and Treatment : Lymphocytes (Pharmacodynamic Population)

Table 14.2.9.1 Summary of Pharmacodynamic Parameters by Treatment : Lymphocyte Subsets (Pharmacodynamic Population)

Table 14.2.9.2 Summary of Pharmacodynamic Parameters by Ethnicity and Treatment : Lymphocyte Subsets (Pharmacodynamic Population)

Safety Data

Adverse Events

Table 14.3.1.1 Overall Summary of Treatment Emergent Adverse Events (Safety Population)

Table 14.3.1.2 Treatment-Emergent Adverse Events by Treatment, System Organ Class and Preferred Term (Safety Population)

Table 14.3.1.3 Treatment-Emergent Adverse Events by Treatment, System Organ Class, Preferred Term and Maximum Severity (Safety Population)

Table 14.3.1.4 Treatment Emergent Adverse Events “Related to IMP” by System Organ Class, Preferred Term and Severity (Safety Population)

Table 14.3.1.5 Treatment Emergent Adverse Events “Not Related to IMP” by System Organ Class, Preferred Term and Severity (Safety Population)

Listing 14.3.2.1 All Serious Adverse Events (Safety Population)

Listing 14.3.2.2 Adverse Events Leading to Discontinuation (Safety Population)

Clinical Laboratory Tests

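### Time to immunoglobulin recovery: the readable measure covers only values that fall below LLN, with no readable rule for subjects not recovered at their last sample and no named output

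*SAP*

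**What the plan says.** SAP 2.2.2 lists "Changes in total serum IgG, IgA and IgM concentrations and time to recovery" among the pharmacodynamic endpoints, which sit under the secondary endpoints. The protocol does the same in 2.2 and 3.2.2.2.

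SAP 4.1.6 states: "And also time to recovery of total serum IgA, IgG and IgM will be analyzed, two measures will be used". Measure 1 is "Time to return to normal range (for those parameters that fall below LLN". The lines after it, where measure 2 would stand, are redacted.

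The readable rules that would govern the analysis are these:

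- SAP 4.3.1 gives each quantitative variable n, mean, SD, median, minimum and maximum unless otherwise stated.
- SAP 4.3.4 opens: "There will be no imputation of missing data done except for defining Treatment Emergent Adverse Event (TEAE", and goes on to add only the prior/concomitant medication classification as a further exception.
- SAP 4.3.8 says of the total immunoglobulins: "observed and change from baseline will be summarized descriptively by treatment [Tables 14.2.7.1 (Immunoglobulin". It adds summaries by ethnicity, individual plots and mean plots, including percent change. Part of the section is redacted.
- SAP section 6 names "Table 14.2.7.1 Summary of Pharmacodynamic Parameters by Treatment : Immunoglobulin (Pharmacodynamic Population" and related tables. The readable pharmacodynamic tables run from 14.2.7.1 to 14.2.9.2, and the figures in section 7 from 14.2.2.1.1 to 14.2.2.9.4, without a gap. None is titled for time to recovery.
- Footnote 2 to the SAP schedule of assessments (section 3.1) provides that if one or more subjects are not back in the normal range by Week 16, "the entire cohort will complete Week 20 and Week 24".

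**The concern.** Two separate problems arise with measure 1.

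**Non-recovered subjects.** The plan foresees subjects who are still low at Week 16, since that is why Weeks 20 and 24 exist. A subject still low at the last sample has a recovery time known only to exceed that visit. A mean or median of the available values leaves that subject out. The loss is greatest wherever recovery is slowest, so differences between groups in duration of effect are compressed.

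**Selection by LLN.** Whether a value crosses LLN is settled after dosing and depends on both baseline and depth of effect. Subjects with a high baseline or a shallow fall never enter measure 1, so dose groups would be compared on different kinds of subject, and a weak-effect dose may contribute one subject or none.

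Duration of effect matters here because protocol 1.3 says that the immunoglobulin data will help refine the PK/PD model and select doses for a repeat-dose study.

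**Working it through.** The documents give no recovery-time figure, so there is nothing to reproduce. Recovery times below are assumptions; reference ranges and visit weeks come from the documents.

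**1. What happens to a subject still low at the last sample.** Under 4.1.6 the time to return is undefined for that subject. Under 4.3.4 nothing is imputed. Under 4.3.1 the summary is of available values. Neither 4.3.8 nor the lists in sections 6 and 7 readably names a censored analysis. On the readable text the subject therefore has no value.

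**2. Size if such subjects are dropped.** Assume lognormal recovery times with true median m and log-SD s, and follow-up to week F.

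- Share recovered: P = Φ(ln(F/m)/s)
- Median among recovered subjects: m × exp(s × z(P/2)), where z is the standard normal quantile

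With F = 24 and s = 0.35:

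| True median (weeks) | P | z(P/2) | Median read (weeks) |
|---|---|---|---|
| 8 | 0.999 | −0.001 | 8.0 |
| 16 | 0.877 | −0.155 | 15.2 |
| 24 | 0.500 | −0.674 | 19.0 |

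The true ratio is 24/8 = 3.0; the ratio read is 19.0/8.0 ≈ 2.4. With s = 0.25 the medians read 8.0, 15.7 and 20.3 (ratio 2.5). With s = 0.50 they read 7.9, 14.0 and 17.1 (ratio 2.2).

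A simulation with 7 subjects per dose, s = 0.35 and recovery seen only at scheduled visits to Week 24 gives:

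| True median (weeks) | Not recovered | Median, dropped | Median, censored |
|---|---|---|---|
| 10 | 0.6% | 11.1 | 12 |
| 14 | 6% | 15.0 | 16 |
| 18 | 20% | 18.2 | 20 |
| 22 | 40% | 20.1 | 24 |

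The gap of 0.9 weeks in the first row cannot come from dropping, because almost everyone recovers. It reflects the coarse visit grid and how the simulated medians were averaged. The excess over about 1 week in the lower rows is the part to attribute to dropping.

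**3. Who enters measure 1.** A fall of fraction f crosses LLN only if baseline is below LLN/(1 − f). The LLNs are 66 mg/dL for IgA and 635 mg/dL for IgG (protocol Table 1).

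- IgA, f = 0.25: 66/0.75 = 88 mg/dL
- IgA, f = 0.50: 66/0.50 = 132 mg/dL
- IgA, f = 0.75: 66/0.25 = 264 mg/dL. The protocol describes this fall as "with a predicted maximal reduction (with repeated dosing) to approximately 75% below baseline" and calls it unlikely after a single dose.
- IgG, f = 0.40 (the fall predicted in protocol 1.3): 635/0.60 ≈ 1058 mg/dL

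To turn this into counts, assume that the IgA range of 66–433 mg/dL is a central 95% lognormal range. The log mean is (ln 66 + ln 433)/2 = 5.130 and the log-SD is (ln 433 − ln 66)/3.92 = 0.480.

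| IgA fall | Baseline limit (mg/dL) | Probability below limit | Expected of 7 |
|---|---|---|---|
| 30% | 94.3 | 0.112 | 0.8 |
| 50% | 132 | 0.303 | 2.1 |
| 70% | 220 | 0.709 | 5.0 |

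For IgG at 40%, with the range 635–1741 mg/dL treated the same way, the expected number is about 3.6 of 7. The immunoglobulin entry limits are redacted; any lower limit on baseline would reduce all these counts.

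**The case against.** The case against has real force on several points.

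- A reader might infer that recovery is measured only in subjects who fall below LLN. The SAP does not support that. It promises two measures, and the second is redacted; it may be relative to baseline and include everyone.
- A reader might also take it as established that recovery will be read too short at the higher doses. No readable text says that non-recovered subjects are excluded. Right-censoring is not imputation, so 4.3.4 is compatible with Kaplan-Meier. A method could stand in the redacted parts of 4.1.6 or 4.3.8. The bias needs both dropping and slow recovery, and protocol 1.3 expects transient effects lasting over weeks.
- Stopping the illustration at Week 16 gives 7.9, 12.6 and 14.0 weeks, about a 1.8-fold difference. That is not the planned case, because footnote 2 takes the whole cohort to Week 24 when anyone is out of range.
- Listings and individual plots with identifiable subjects are planned, so a non-recovered subject would be visible.
- With one or two qualifying subjects at a dose, a Kaplan-Meier median says little.

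These points make the bias conditional, reduce its size and limit where a median is worth reporting. They do not supply a readable censoring rule. Nor would a redacted definition in 4.1.6 account for the absence of a recovery title from unbroken table and figure lists. Plots let a reader see slow recovery but do not analyse the endpoint.

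**Conclusion.** The point stands in limited form. For measure 1, the readable SAP names a secondary endpoint and a post-dosing subset, but no treatment of non-recovery and no output. Its stated defaults leave non-recovered subjects without a value.

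If they are dropped and recovery is slow, the plan's 24-week follow-up gives about 8.0, 15.2 and 19.0 weeks for true medians of 8, 16 and 24: roughly 2.4-fold instead of 3-fold, and 2.2- to 2.5-fold for log-SD from 0.50 to 0.25. If nearly all subjects recover by Week 24, the distortion is negligible. These medians and spreads are assumptions, not figures from the documents, and the direction of bias follows recovery speed rather than dose as such.

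The LLN restriction is a distinct problem of comparability. It mainly removes subjects with shallow falls, who are likely to be at the lower doses. The counts rest on an assumed lognormal baseline and ignore the redacted entry limits.

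The SAP should be amended, because a better analysis is available from data already planned and the handling should be fixed before unblinding.

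**What to change.** Unless the redacted text already does so:

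1. In SAP 4.1.6 and 4.3.8, state the time origin for measure 1 and analyse it by Kaplan-Meier per dose for IgA, IgG and IgM, right-censoring non-recovered subjects at their last immunoglobulin sample.
2. Report per dose the numbers who fell below LLN, recovered and were censored. Give a median with confidence interval only where numbers allow.
3. Present this beside the second measure, or beside a baseline-relative measure if the redacted one is not of that kind, so that subjects who never cross LLN also contribute.
4. Add the table to SAP section 6 and the figure to section 7.

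The cost is SAP wording, one table and one figure, with no new samples or visits. The downside is that some medians will not be estimable in small groups; the counts will then carry the information.
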